## **5.5 Dissemination of Data**

Results of this study may be used for presentations, posters, grant applications, or publications. The publications will not contain any identifiable information that could be linked to a subject.

## **5.6 Data Handling and Recordkeeping**

Source documents and paper CRFs will be stored in a secure area of the PI's laboratory. Access will be limited to study personnel. When eventually destroyed, paper documents will be shredded per UAMS disposal guidelines. At no time shall Protected Health Information be released to non-study personnel. Coded data (results from blood sample analyses) will be stored in an Excel file kept on the UAMS/RSCOA server (requires secure access). These data files do not contain PHI or identifiers; the code to subjects is also kept in an Excel file on the UAMS/RSCOA server. These files will be kept indefinitely.

## **5.7 Data Access**

All study subject material will be assigned a unique identifying code or number. The key to the code (the instrument associating the data with subject identity) will be kept on a password protected UAMS server, located behind locked doors in a restricted access area of the UAMS campus. Only those individuals listed on the title page of this protocol and their research staff members will have access to the code and information that identifies the subject in this study. This file will be deleted approximately seven years after data analysis is completed.

---

## **6.0 Risks and Benefits**

---

There are no guaranteed benefits for the subjects. Anticipated risks associated with this protocol are described in detail below. All experimental procedures will be performed by appropriately trained and credentialed personnel. The PI and/or study physician will be responsible for oversight of study procedures and evaluation of adverse events.

### **6.1 COVID-19 Protections**

Subjects will undergo the current screening procedures in place for UAMS patients at the time of their visits. Visitors will not be permitted unless UAMS policy changes permit them. Subjects will be required to wear a suitable facemask for the entirety of their study

visits except when ingesting their isotopes/SP. Study staff will wear their mandated masks and use universal blood-borne precautions while handing blood samples.

Study visit areas are disinfected after study visits as per protocol.

## **6.2 Blood sampling/IV insertion**

Blood samples will be collected solely for the purpose of experimentation. The total amount of blood taken will be up to 60 mL. Subjects should have no noticeable effects of this volume of sampling. Brief discomfort due to the IV insertion is common. There is also a risk of possible bruising, redness, and swelling at the IV site. There is also a possibility of feeling lightheaded when the IV is inserted or, less commonly, fainting. Finally, there is the rare risk of infection due to the IV. The subject's heated arm will be monitored for signs of skin injury. Subject's arm will be inside a pillowcase when using the hot plastic box method, with its thermostat set no higher than 55 degrees Centigrade. Heating pad will be used on the highest setting available.

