### 1.0 Protocol Summary

---

This will be a double-blinded, randomized, crossover pilot study to evaluate the validity of a continuous oral sip-feeding of stable isotope tracer method for the evaluation of whole-body protein metabolism. This method will be evaluated using two different amounts of an essential amino acid (EAA) + whey protein supplement on up to ten younger, healthy subjects. Stable isotope preparations will be continuously consumed by subjects throughout visits 2 and 3 to enable whole body protein metabolism to be measured. A DXA scan will be performed to quantify subject's lean mass.

---

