### **4.0 Study Population**

---

Up to 10 subjects of any gender or ethnicity will be enrolled with a target of n=10, 50% female for study completion. Subjects' duration of participation is approximately 2 weeks.

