#### **4.5 Study Visits**

Visit 1: This visit will take place at the UAMS RIOA.

At this visit, informed consent discussion is held. Study staff will use appropriate PPE with surgical mask and gloves. Subjects will also be required to wear a mask and if they do not have one, a mask will be provided to them by the study staff. If a subject enrolls, their eligibility will be determined. Eligible subjects will be randomized and be scheduled for Visit 2. A whole body DXA scan will be performed by study staff using the PI's machine for quantification of lean mass.

Visit 2: This visit will take place at the UAMS IOA. Subjects will be instructed to fast (consuming only water) from 10:00 P.M. the evening prior to this visit. Study nurse will insert an IV into the subject's preferred arm. At scheduled intervals, study staff will draw a ~2mL blood sample from the IV for research purposes, warming the arm by means of a heating pad or a heated plastic box. Blood will be transferred into a blood collection tube that contains EDTA, cooled on wet ice, centrifuged at  $\geq$  3000 RPM for  $\geq$  6 minutes, and have the resultant plasma transferred to a labelled cryo tube for freezing at  $\leq$  -80 degrees Centigrade.

After the initial blood sample is drawn, subjects will begin ingesting their oral isotope preparations, beginning with a priming dose (per study-specific stable isotope calculations). A timer will start when the priming dose is ingested. At 10-minute intervals, subjects will ingest a smaller volume of stable isotope preparations that will continue throughout the duration of the study visit (approximately 7 hours).

Approximately three hours after study initiations, subjects will ingest their randomly chosen amount of SP. Blood sample collection will continue at specific intervals throughout the remainder of Visit 2.

At the conclusion of the 7-hour study visit, the IV will be removed and a bandage placed over the site. Subjects will be provided with snacks and a beverage and be free to leave the site. Visit 3 is scheduled.

Visit 3: Subjects will come back to the RIOA having fasted overnight as for Visit 2. All study procedures undertaken during Visit 2 will be repeated at Visit 3, with subjects ingesting the remaining SP amount.

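### Section 6.2 sends the heating pad to its top setting without the cloth barrier given to the box and without permission to turn it down: a minor participant-safety point with a near-costless wording fix

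*Combined protocol and SAP*

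**What the plan says.** Arm warming appears in two places in the combined protocol and SAP.

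- Section 4.5 (Study Visits), in the sentence on drawing samples at scheduled times, provides for "warming the arm by means of a heating pad or a heated plastic box". Visit 3 repeats the Visit 2 procedures.
- Section 6.2 (Blood sampling/IV insertion) sets the conditions. For the box: "Subject's arm will be inside a pillowcase when using the hot plastic box method", "with its thermostat set no higher than 55 degrees Centigrade". For the pad, in the next sentence: "Heating pad will be used on the highest setting available". For both devices: "The subject's heated arm will be monitored for signs of skin injury".

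Section 6.0 adds that trained, credentialed personnel carry out the procedures, overseen by the investigator and/or study physician. It also says that subjects have no guaranteed benefit. Section 6.5 has staff ask about adverse events at both sampling visits and record them in the case report form.

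**The concern.** The protocol treats arm heating as something that can injure skin: it calls for monitoring and gives one of the two permitted devices a cloth barrier and a temperature limit. The other device receives neither, and staff are told to run it at its maximum. That sentence is an instruction, so the problem is more than an omitted detail. Read literally, it leaves staff no discretion to choose a milder setting, and no other section supplies any.

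Monitoring for injury works by noticing a change and reacting to it. A barrier, and freedom to lower the heat when the subject finds it uncomfortable, act earlier. What is at stake is avoidable discomfort or minor skin injury in volunteers who gain nothing certain from taking part.

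**Working it through.** No power, sample-size or error-rate figure is involved. The check is a comparison of the text for the two devices, followed by a count of how often arm warming could occur.

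**Side-by-side reading**

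| Safeguard | Heated box | Heating pad |
|---|---|---|
| Cloth barrier | Pillowcase (6.2) | None stated |
| Limit on heat | Thermostat at most 55 degrees Centigrade (6.2) | None stated; top setting directed (6.2) |
| Leave to reduce or stop heat | None stated | None stated; top setting directed |
| Monitoring for skin injury | Yes (6.2) | Yes (6.2) |
| Trained staff and oversight | Yes (6.0) | Yes (6.0) |

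The pillowcase and the 55-degree limit are tied by their wording to the box, so they cannot be read across to the pad. The monitoring sentence refers to the heated arm without naming a device, so it covers both.

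**Scope of arm warming**

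Inputs: at most 10 subjects (Section 4.0: "Up to 10 subjects of any gender or ethnicity will be enrolled"); two sampling visits each (4.5); 15 samples per visit of about 2 mL (5.1).

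1. Check of the sampling figures against the plan's own total: 15 samples × 2 mL × 2 visits = 60 mL per subject, which agrees with Sections 5.1 and 6.2.
2. Visits with arm warming: 10 × 2 = up to 20.
3. Samples: 15 × 2 = 30 per subject; 30 × 10 = up to 300.
4. The split between pad and box is not stated, so pad use lies anywhere from 0 to 20 visits, or 0 to 300 samples.

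**Opportunity to report discomfort**

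Section 4.5: "At 10-minute intervals, subjects will ingest a smaller volume of stable isotope preparations", over about 7 hours. That is 420 min ÷ 10 min = about 42 sips per visit. Subjects are therefore awake, and they are described in Section 1.0 as "up to ten younger, healthy subjects" (aged 21 to 40 under Section 4.1). This counts as mitigation.

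**What cannot be computed**

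The documents do not give the pad's maximum temperature, the time the arm is heated, or whether the pad touches bare skin. No injury rate follows from them, and neither does a difference in risk between pad and box or a reduction due to the fix. The counts above describe occasions of use, not the size of a hazard.

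**The case against.** The case for leaving the text alone has real weight.

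- **No harm is shown.** Temperature, contact time and skin contact are all unstated, and pad use could be zero. Whether warming is continuous or brief around each draw is not stated either, and burn risk would depend on that. This stands in full.
- **The comparison with the box may mislead.** A box with an adjustable thermostat needs a number; a pad with fixed settings is bounded by its own maximum. A reader might infer that the pad is hotter or more dangerous than a box allowed up to 55 degrees. The documents do not support that inference, because the pad's maximum is unknown. Equally, they do not show that the maximum is low enough to stand in for a stated limit.
- **The risk is already managed.** Trained staff watching for skin injury would be expected to act on what they see, and an awake subject can speak up. This largely stands, and it keeps the point minor. It does not remove the written direction to use the top setting, and the protocol does not say that discomfort alone is a reason to turn the pad down.
- **A lower setting may affect sampling.** The documents do not say how warm the arm must be, and a comfort-based setting could differ between a subject's two visits. This stands as a caution. It does not touch the cloth barrier or the stop rule.

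A reader might also infer that the arm-warming instruction weakens the comparison of oral and infused tracer in Section 5.4. Nothing in the documents links the two, and no such claim is made here.

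**Conclusion.** The point holds as a minor, participant-safety improvement. Section 6.2 directs the pad to its highest setting and, unlike for the box, states no skin barrier and no leave to turn it down. Monitoring and trained staff already mitigate this, and no excess risk over the box can be shown.

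The reading of the text is certain; the safety gain from changing it is plausible but cannot be quantified. The conclusion assumes that staff would follow the sentence as written, and that no site procedure outside these documents already supplies a barrier or a turn-down rule. If the pad is never used, the point has no practical effect.

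**What to change.** Replace the pad sentence in Section 6.2 with:

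> *The heating pad will be used over a cloth barrier, such as the pillowcase used for the box, at a setting no higher than is comfortable for the subject. With either device, heat will be reduced or stopped at subject-reported discomfort or any sign of skin injury.*

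I would not add a numeric ceiling for the pad, a rule to use the lowest setting that warms the arm adequately, or a maximum fixed by the study physician. The documents give no temperature, no criterion for adequate warming and no basis for choosing a maximum.

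The cost is two sentences in place of one, and a pillowcase of the kind already in use. The downside is that the arm may warm more slowly or somewhat less with the pad; the effect on sampling is unknown. If the pad at a comfortable setting does not suffice, the box remains available under Section 4.5.

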## **6.3 Confidentiality**

A potential risk to study participants is the loss of confidentiality. Measures to protect the confidentiality of study participants will be implemented as described in the Data Handling and Recordkeeping section above.

## **6.4 Study Products**

The SP contains whey protein and may contain a small amount of lactose. Subjects with a known allergy or intolerance to whey protein, milk or lactose should not participate. In subjects with these allergies/intolerances, side or adverse effects of SP would include: abdominal pain, bloating, rash or hives, red and watery eyes, a runny nose, sneezing and coughing, diarrhea, nausea, and intestinal cramps.

The amino acids are naturally occurring required nutrients with no known adverse effects, even at much higher doses than will be used in this protocol. They are classified

as GRAS by the FDA. Study staff are responsible for accountability and dispensing of SP.

## **6.5 Adverse Events**

- Study staff will ask subjects about the occurrence of adverse events during visits 2, 3, and the follow-up calls after these visits.
- Possible side effects of the SP listed above will be documented as an adverse event. Any allergic reaction to the SP will be treated as an adverse event.
- The PI and study physician are responsible for reviewing and evaluating adverse events.
- Adverse events will be recorded in the CRF and on an excel spreadsheet that is submitted to the IRB at required intervals.
- Serious adverse events will be reported to the IRB within 24 hours of their discovery.

## **6.6 DXA Scan**

A whole body DXA scan will be performed one time per subject. The radiation exposure for a single scan is approximately half that of a chest x-ray.

---

## **7.0 Ethical Considerations**

---

This study will be conducted in accordance with all applicable government regulations and University of Arkansas for Medical Sciences (UAMS) research policies and procedures. This protocol and any amendments will be submitted and approved by the UAMS Institutional Review Board (IRB) to conduct the study.

The formal consent of each subject, using the IRB-approved consent form, will be obtained before that subject is submitted to any study procedure. All subjects for this study will be provided a consent form describing this study and providing sufficient information in language suitable for subjects to make an informed decision about their

participation in this study. The person obtaining consent will thoroughly explain each element of the document and outline the risks and benefits, alternate treatment(s), and requirements of the study. The consent process will take place in a quiet and private room, and subjects may take as much time as needed to make a decision about their participation. Participation privacy will be maintained and questions regarding participation will be answered. No coercion or undue influence will be used in the consent process. This consent form must be signed by the subject and the individual obtaining the consent. A copy of the signed consent will be given to the participant, and the informed consent process will be documented in each subject's research record.

---

